#### 11.4.6. Changes to Planned Analyses

Any changes to the planned statistical analyses made prior to performing the analyses will be documented in an amended Statistical Analysis Plan approved prior to performing the analyses. Changes from the planned statistical methods after performing the analyses will be documented in the clinical study report along with a reason for the deviation.

# 12. Health Economics Outcomes

A formal health economics analysis may be completed as part of this trial study, given meaningful clinical results are obtained. This will take into consideration complication rates, quality of life, and resource utilization. The EQ-5D-5L, generic quality of life measure, will be used to assess health utilities. We may estimate costs associated with the health care utilization measures at all sites. These inputs may be used in health economics analysis performed.

# 13. Data Management

## 13.1.Data Collection, Processing, and Review

Subject data will be recorded in a limited access secure electronic data capture (EDC) system.

The clinical database will reside on a production server hosted by Medidata EDC System. All changes made to the clinical data will be captured in an electronic audit trail and available for review by the sponsor or its representative. The associated Rave software and databases used in this clinical study have been designed to meet regulatory compliance for deployment as part of a validated system compliant with laws and regulations applicable and to the conduct of clinical studies pertaining to the use of electronic records and signatures. Database backups will be performed regularly.

The Investigator provides his/her electronic signature on the appropriate electronic case report forms (eCRFs) in compliance with local regulations. A written signature on printouts of the eCRFs will also be provided only if required by local regulation. Changes to data previously submitted to the sponsor require a new electronic signature by the Investigator acknowledging and approving the changes.

Visual and/or electronic data review will be performed to identify possible data discrepancies. Manual and/or automatic queries will be created in the Medidata EDC system and will be issued to the site for appropriate response. Site staff will be responsible for resolving all queries in the database.

Data transfers from other systems such as the Rhythmia HDx System or core labs will be coordinated by Boston Scientific.

All access to the clinical database will be changed to "Read only" after all data is either "Hard Locked" or "Entry Locked". Once acceptance of the final report or finalization of publications (as applicable) is received, final database storage and archiving activities can begin. Once all the closeout activities are completed a request to IT is submitted to have the "Database Locked" or Decommissioned and all database access revoked.

#### 13.2. Data Retention

The Principal Investigator or his/her designee or Investigational site will maintain all essential study documents and source documentation that support the data collected on the study subjects in compliance with applicable regulatory requirements.

The Principal Investigator or his/her designee will take measures to prevent accidental or premature destruction of these documents. If for any reason the Principal Investigator or his/her designee withdraws responsibility for maintaining these essential documents, custody must be transferred to an individual who will assume responsibility and BSC must receive written notification of this custodial change. Sites are required to inform Boston Scientific in writing where paper or electronic files are maintained in case files are stored off site and are not readily available.

#### 13.3. Technical Source Forms

The Boston Scientific study team will create a Technical Source Form (TSF) to capture protocol required data elements that are not located in any other source documents. The TSF will be provided to the study sites for use as a source document. The protocol trained Boston Scientific representative may only use study-specific TSFs provided and approved by the Boston Scientific study team. Data collected on any site created worksheets must not be attributable to the Boston Scientific representative. The Boston Scientific representative providing technical support is not part of the site study team.

General TSF documentation considerations for the protocol trained Boston Scientific representative are as follows:

- Data that is collected as part of a clinical study must be attributable to the individual collecting/providing the data, and must include the individual's name, signature, and date of signature.
- Boston Scientific Representative involvement with data collection/providing source documentation should be minimized.
- Any source data collected to capture protocol required data elements by a Boston Scientific representative must be provided to a member of the study team at the conclusion of the visit and retained at the site.
- The Boston Scientific representative and Research Coordinator must make arrangements in advance as to how the clinical trial data will be transferred from the Boston Scientific representative to a member of the study team.
- The Boston Scientific representative completes the sections of the TSF that are appropriate to his/her role only (e.g., technical sections.)
- The Boston Scientific representative signs and dates completed sections of the TSF applicable to the Boston Scientific representative role. The Boston Scientific representative may assist in obtaining the signature and date of the Investigator or clinical research site staff delegated by the Investigator to oversee the study activity.

Collection and completion of all information on the TSF is the responsibility of the appropriate personnel as defined on the TSF. If available, the protocol trained Rhythmia mapping specialist or other protocol trained Boston Scientific representative will provide the delegated site personnel with the study related data collected during the case directly from the Rhythmia HDxTM system.

At the conclusion of the procedure, the completed technical source form must be signed (and initialed as needed) by the following people:

- Delegated Site Personnel completing the forms
- Delegated Investigator conducting and/or supervising the case
- BSC personnel supporting the visit

#### 13.4. Core Laboratories

#### 13.4.1. Event Monitors

A Core Lab will provide the center with all necessary instructions and/or materials related to the use of the event monitor. It is the responsibility of the site personnel/center to educate the subject on how to use the event monitor. If the subject is unable to submit their heart rhythms, core lab personnel may contact the subject to troubleshoot any issues with the event monitor. Only TREATMENT subjects will be provided with an event monitor. The event monitor will be provided to the subject prior to discharge from the hospital or at the 1-month visit. All events will be analyzed by the centralized research company to determine if the episodes are associated with arrhythmia recurrence. The Core Lab will make this information accessible to the Investigator center for concurrence. The third-party cardiologist will be used for final rhythm determination and final adjudication of the event.

Within the first 90 days (3 months) after the index ablation procedure (blanking period), TREATMENT subjects will be instructed to transmit all symptomatic episodes for detection and/or treatment of early recurrences. After the subject's 3-month follow-up visit, subjects will be instructed to send at least two transmissions per month (either symptomatic or asymptomatic) through the 12-month follow-up to ensure continued reporting compliance. If subjects experience symptoms associated with cardiac arrhythmias (e.g. palpitations, lightheadedness, syncope, dyspnea), they will be instructed to transmit a recording. Such recordings will count towards the required transmission of that period. The Core Lab will work with the investigational site to ensure reporting compliance.

All event monitors should be returned to the Core Lab or the Sponsor upon completion of a subject's 12-month follow-up or withdrawal from the study.

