# Clinical Evaluation of the StablePoint Catheter and Force-Sensing System for Paroxysmal Atrial Fibrillation (NEWTON AF) 90% 90% 90% Power 160 183 288 Sample size \*12-Month Effectiveness will only be evaluated as a secondary endpoint if the primary effectiveness objective is fulfilled at the 6-Month Primary Effectiveness analysis. This study will employ a rhythm surveillance monitoring strategy Arrhythmia consistent with the recommendations in the 2017 HRS expert consensus Monitoring statement on catheter and surgical ablation of atrial fibrillation. A wearable Strategy arrhythmia/event monitor will be used to assess atrial arrhythmia recurrence (including unscheduled visits for symptomatic atrial arrhythmias and 24-hour Holter monitoring at the 6- and 12-month followup). Within the first 90 days after the index ablation procedure, TREATMENT subjects will be instructed to transmit all symptomatic episodes for detection and treatment of early recurrences. All TREATMENT subjects will be provided with an event monitor and required to submit at least two transmissions every month after their 3-month follow-up visit until their 12-month follow-up. All TREATMENT subjects will be provided with a 24-hour Holter Monitor at the 6-month follow-up visit where they will be required to submit their heart rhythms. Another 24-hour Holter is required at the 12month follow-up visit. A core lab will be utilized for reviewing electrocardiographic recordings from the surveillance monitoring, inclusive of data from the wearable arrhythmia/event monitors and in-hospital ECGs.

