# 6.3. Primary Effectiveness Endpoint at 6 Months

The primary effectiveness endpoint at 6 months is defined as the effectiveness event-free rate at 6 months (183 days) post-procedure. If the analysis of the primary effectiveness endpoint at 6 months is not passed, then effectiveness may be re-evaluated via the primary effectiveness endpoint at 12 months, as described in Section 6.6.

Primary effectiveness events at 6 months are defined as:

- Acute procedural failure
  - Failure to achieve acute procedural success in the index procedure or in a repeat procedure during the blanking period.
  - Acute procedural success is defined as the achievement of electrical isolation of all PVs using the StablePoint catheter only. Electrical isolation of a PV is demonstrated by entrance block after 20 minutes waiting period. If exit block testing is performed, the PV will only be considered as isolated if both entrance and exit block testing are successful.

- Use of amiodarone post index procedure
- Use of non-study ablation catheter in the index procedure or in a repeat procedure during the blanking period
- More than one repeat procedure during the blanking period (90 days post index procedure)
- Surgical ablation of Atrial Fibrillation (AF)/Atrial Tachycardia (AT)/Atrial Flutter (AFL) post index procedure
- Documented atrial fibrillation, or new onset of atrial flutter or atrial tachycardia between 91 days and 183 days post index procedure captured by one of the following methods:
  - > 30 seconds in duration recording from the study specific event monitor or Holter Monitor
  - ≥ 10 second 12-lead Electrocardiography (ECG)
- Any of the following interventions for atrial fibrillation, or new onset of atrial flutter or atrial tachycardia between 91 days and 183 days post index procedure:
  - Repeat procedure
  - Electrical and/or pharmacological cardioversion
  - Prescribed any AAD\*
- \*AADs for endpoint will consist of all Class I/III, including Amiodarone, and any Class II/IV medications taken for control of atrial fibrillation (AF)/Atrial tachycardia (AT)/Atrial flutter (AFL) recurrence.

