# 6.5. Primary Effectiveness Endpoint at 12 Months

The primary effectiveness endpoint at 12 months is defined as the event-free rate at 12 months (365 days) post-procedure.

Primary effectiveness events at 12 months are defined as:

- Acute procedural failure
  - Failure to achieve acute procedural success in the index procedure or in a repeat procedure during the blanking period.
  - Acute procedural success is defined as the achievement of electrical isolation of all PVs using the StablePoint catheter only. Electrical isolation of a PV is demonstrated by entrance block after 20 minutes waiting period. If exit block testing is performed, the PV will only be considered as isolated if both entrance and exit block testing are successful.
- Use of amiodarone post index procedure
- Use of non-study ablation catheter in the index procedure or in a repeat procedure during the blanking period.
- More than one repeat procedure during the blanking period (90 days post index procedure)
- Surgical ablation of Atrial Fibrillation (AF)/Atrial Tachycardia (AT)/Atrial Flutter (AFL) post index procedure
- Documented atrial fibrillation, or new onset of atrial flutter or atrial tachycardia between 91 days and 365 days post index procedure captured by one of the following methods:
  - ≥ 30 seconds in duration from the study specific event monitor or Holter Monitor

- ≥ 10 second 12-lead Electrocardiography (ECG)
- Any of the following interventions for atrial fibrillation, or new onset of atrial flutter or atrial tachycardia between 91 days and 365 days post index procedure:
  - Repeat procedure
  - Electrical and/or pharmacological cardioversion
  - Prescribed any AAD\*

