# 10.4.1.2. AADs post Index Procedure during the 90-day blanking period

Blanking period is defined as the time between Index procedure and 90 calendar days post Index procedure. Post-procedure AADs are allowed per physician's discretion during the blanking period. New AADs should not be prescribed unless considered medically necessary. If treatment with AAD is prescribed during the blanking period, it is recommended that a Class I or III AAD be selected according to the ACC/AHA/ESC 2014 Guidelines for the Management of Patients with AF. No amiodarone use is permitted post procedure. After the index procedure, it is recommended that the Investigator removes subjects from AADs to appropriately assess the subject for early arrhythmia recurrence that may require a repeat ablation procedure within the blanking period (on or before day 90 post index procedure).

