### 10.6.5. Three Month Follow-Up Visit (91 days +/-14 days)

The 3-month Follow-up Visit must occur within 91  $\pm$ 14 days post Index Procedure.

The data collection at the three-month follow-up visit includes:

- Date of visit
- Quality of Life Instruments (AFEQT and EQ-5D-5L). It is highly recommended that these assessments be completed prior to the remaining clinical assessments (e.g., 12lead ECG and physical assessment).
- Physical assessment performed as standard of care including temperature, O2 saturation, weight, resting heart rate, systolic and diastolic blood pressure
- Rhythm at time of visit by means of a 12-lead ECG

- 5) Review of any symptomatic transmissions from event monitor that occurred prior to 3-month visit and
  - Review expectations for arrythmia/event monitor transmissions with subjects (e.g. subjects are required to submit their heart rhythms, symptomatic and asymptomatic, a minimum of twice per month)
- Documentation of any intervention for AF/AT/AFL (e.g. Repeat Procedure, Cardioversion), if applicable
- Subjects with unresolved phrenic nerve palsy detected at the discharge visit must be reassessed per center's standard of care to evaluate if the event resolved
- Perform Cardiac CT/MRI if PV stenosis is suspected at any time throughout the followup period
- New, discontinued or changes in study-collected medication information (e.g. AAD and NOAC)
- Reportable Adverse Events, including resolution of ongoing events, if applicable
- 11) Protocol Deviations, if applicable

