## 10.6.7. Twelve Month Follow-Up Visit (365 days $\pm$ 30 days)

The 12-month Follow-up Visit must occur within 365 days  $\pm$  30 days post Index Procedure.

The data collection at the 12-month follow-up visit includes:

- Date of visit
- Quality of Life Instruments (AFEQT and EQ-5D-5L). It is highly recommended that these assessments be completed prior to the remaining clinical assessments (e.g., 12lead ECG and physical assessment).
- Physical assessment performed as standard of care including temperature, O2 saturation, weight, resting heart rate, systolic and diastolic blood pressure
- Rhythm at time of visit by means of a 12-Lead ECG
- 5) Collection and review of any symptomatic or asymptomatic events (via event monitor and 24-hour Holter). If the subject did not apply the 24-hour Holter prior to the 12month visit, please apply the 24-hour Holter to the subject during the visit and request the subject submit their heart rhythm and to return the 24-hour Holter monitor after the assessment is complete.
- Documentation of any intervention for AF/AT/AFL (e.g.: Repeat Procedure, Cardioversion), if applicable
- 7) Perform Cardiac CT/MRI if PV stenosis is suspected at any time throughout the follow-up period
- Subjects with unresolved phrenic nerve palsy detected at the discharge visit must be re-assessed per center's standard of care to evaluate if the event resolved
- New, discontinued or changes in study-collected medication information (e.g. AAD) and NOAC)
- Reportable Adverse Events, including resolution of ongoing events, if applicable
- Protocol Deviations, if applicable

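### Scheduled event-monitor transmissions follow the 3- and 12-month visits rather than days 91 and 365, leaving a small, device-favouring sampling gap at each end of the effectiveness window

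*Combined protocol and SAP*

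**What the plan says.** The endpoint runs on a fixed clock. Section 6.3 counts "Documented atrial fibrillation, or new onset of atrial flutter or atrial tachycardia between 91 days and 183 days post index procedure", and Section 6.5 uses the same wording with day 365 as the end. Section 10.4.1.2 fixes the end of blanking in calendar days: "Blanking period is defined as the time between Index procedure and 90 calendar days post Index procedure".

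The scheduled, symptom-independent transmissions run on a visit clock. Under Arrhythmia Monitoring Strategy, the Synopsis has subjects "required to submit at least two transmissions every month after their 3-month follow-up visit until their 12-month follow-up". Section 13.4.1 agrees: "After the subject's 3-month follow-up visit, subjects will be instructed to send at least two transmissions per month". The visit windows are 91 ± 14 days (Section 10.6.5) and 365 ± 30 days (Section 10.6.7). On return of the device, Section 13.4.1 says: "All event monitors should be returned to the Core Lab or the Sponsor upon completion of a subject's 12-month follow-up". Sections 7.1, 9.6 and 10.9 treat participation as complete once the 12-month visit and its 24-hour Holter are done. No section ties transmissions or monitor return to day 91 or day 365.

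Other observation does continue. Symptom-triggered recording is requested through the first 12 months (Sections 10.6.8 and 13.4.1), and the 3-month visit includes a 12-lead ECG.

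On analysis, Section 11.1.5.3 gives a 12-month censoring rule only for subjects who withdraw or die. Section 11.1.3.3, for 6 months, also censors event-free subjects still active at the data snapshot, at the later of last visit and monitor use.

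**The concern.** Section 11.1.3.2 states that asymptomatic as well as symptomatic events count, and it adjusts the studies behind the 6-month performance goal for this. Scheduled transmissions are the main means of finding asymptomatic episodes between visits. A fully compliant subject seen at 3 months on day 105 owes none on days 91-104, although the window is open.

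A subject whose 12-month visit falls on day 335 can complete the study and return the monitor, and nothing in the plan then collects data for days 336-365. That loss covers symptomatic recurrence and interventions as well as asymptomatic episodes.

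Any recurrence missed this way favours the device. In a single-arm comparison with a fixed goal, no control arm is subject to the same loss.

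**Working it through.** **Plan's own figures.** For one proportion, n = (z₀.₉₇₅√(p₀q₀) + z₀.₉₀√(p₁q₁))² / (p₁ − p₀)², rounded up, then divided by 0.90 for 10% attrition.
- 6 months (60% vs 72%): 164, and 164/0.90 gives 183, as in Section 11.1.3.2.
- 12 months (50% vs 60%): 259, and 259/0.90 gives 288, as in Section 11.1.5.2.

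Both reproduce, and neither changes below.

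**Windows.** Days 91-183 are 93 days; days 91-365 are 275 days.

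**Gap per subject.** Start gap = max(0, 3-month visit day − 91). End gap = max(0, 365 − 12-month visit day).

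| Visit | Day | Gap (days) | Share of 6-month window | Share of 12-month window |
|---|---|---|---|---|
| 3-month | 77 to 91 | 0 | 0% | 0% |
| 3-month | 98 | 7 | 7.5% | 2.5% |
| 3-month | 105 | 14 | 15.1% | 5.1% |
| 12-month | 335 | 30 | none | 10.9% |
| 12-month | 350 | 15 | none | 5.5% |
| 12-month | 365 to 395 | 0 | none | 0% |

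The combined maximum of 44/275 = 16.0% needs one subject at both extremes. At two transmissions per 30.4 days, 14 days is about one of the six due by day 183, and 44 days is about three of the 18 due by day 365.

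**Average gap if visits are spread evenly over their windows (assumption).** Start: (1 + … + 14)/29 = 105/29 = 3.6 days, or 3.9% of the 6-month window. End: (1 + … + 30)/61 = 465/61 = 7.6 days. Both together: 11.2/275 = 4.1% of the 12-month window.

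**Bias if only asymptomatic events are missed.** Section 11.1.3.2 gives a 2.9% relative loss in the ZERO AF 6-month event-free rate when asymptomatic events are added. By arm it is 1.8% (72.9 to 71.6) and 3.9% (79.1 to 76.0). I assume that events are spread evenly over the window, that every asymptomatic event in the gap is lost, and that the 6-month figure also applies at 12 months. With r the relative loss and p₀ the goal, the asymptomatic share is p₀/(1 − r) − p₀, and the bias is that share times the gap fraction.
- 6 months, r = 1.8% to 3.9%: share 1.10 to 2.43 points. With all visits on day 105, times 14/93 gives 0.17 to 0.37 points. With even spread, at most 2.43 × 3.9% = 0.10 points.
- 12 months: share 0.92 to 2.03 points. With all visits at both worst days, times 44/275 gives 0.15 to 0.33 points. With even spread, at most 2.03 × 4.1% = 0.08 points.

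By normal approximation with 164 and 259 evaluable subjects, one-sided type I error moves from 0.025 to 0.028-0.031 (6 months) or 0.028-0.032 (12 months) at the worst days. With even spread it is at most 0.027.

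**End gap if early completers are carried as event-free to day 365.** The planned rates fall from 72% at day 183 to 60% at day 365, which is 12 points over 182 days. If events are evenly spread, a day-335 exit hides 12 × 30/182 = 2.0 points of event risk for that subject. With evenly spread visits the average is 12 × 7.6/182 = 0.5 points. At the 50% goal with 259 evaluable subjects, that moves one-sided type I error to about 0.036. If early completers are instead censored at last contact, and leaving early is unrelated to risk, this bias disappears.

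**The case against.** Four stronger readings are tempting, and the documents do not support them.

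- **Only symptomatic episodes are requested until the 3-month visit.** The Synopsis and Section 13.4.1 limit that instruction to the first 90 days. From day 91 to a late visit the text is silent on scheduled transmissions; it does not restrict them to symptoms.
- **The start of the window is unsampled.** Symptom-triggered recording continues, a 3-month visit after day 91 brings a 12-lead ECG inside the window, and interventions count from day 91 whatever the monitor schedule. What is lost is about one scheduled transmission.
- **Missed recurrences count as success.** A recurrence missed on days 91-104 and found later by transmission, ECG or Holter still makes the subject a failure. Only a subject with no later detection escapes.
- **The 12-month rate is inflated by 0.5 to 2.0 points.** That requires early completers to be carried as event-free to day 365. Section 11.1.5.3 does not say this, and it would depart from the censoring principle in Section 11.1.3.3. The 2.0 points also describe one subject leaving on day 335, not the study average.

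It can also be said that Section 11.3.2.1 calls the surveillance equivalent to that of recent studies of the same kind. If their schedules were visit-based too, part of the loss is already in the 6-month goal. The documents do not allow that to be checked.

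These points limit the size. The mismatch remains: a site following the text exactly leaves part of a primary endpoint window without scheduled sampling, and the 12-month analysis has no stated rule for early completers.

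**Conclusion.** The point holds as a minor one, with a cheap improvement available. Scheduled transmissions can be absent for up to 14 of 93 days at the start of the 6-month window. A subject with an early 12-month visit can be unobserved for up to 30 of 275 days, which cannot affect the 6-month endpoint. Only 3-month visits after day 91 or 12-month visits before day 365 create a gap.

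On the plan's own asymptomatic figure, the inflation is at most about 0.4 points with every visit on the worst day and about 0.1 points with even spread, against planned margins of 12 and 10 points. This assumes evenly spread events and a ZERO AF reduction that carries over; that figure could understate asymptomatic recurrence, since it reflects another study's monitoring. The further 0.5-point average at 12 months is conditional on a handling of early completers that the plan neither states nor excludes.

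**What to change.** In the Synopsis (Arrhythmia Monitoring Strategy) and Section 13.4.1, require the twice-monthly transmissions from day 91 whatever the date of the 3-month visit, through the later of day 365 and the 12-month visit. Give the instruction by the 1-month visit, by which time the subject should have the monitor. Have the monitor returned only after both dates. Align the completion wording in Sections 7.1, 9.6 and 10.9.

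In Section 11.1.5.3, state that event-free subjects who complete before day 365 are censored at their last visit or monitor use, whichever is later, as Section 11.1.3.3 does for active subjects.

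The cost is wording in these sections and in the subject instructions, and up to 30 more days with the monitor for some subjects. No new device or visit is needed, and the sample sizes stand. The longer loan captures only monitor-recorded rhythm. Interventions after an early 12-month visit are left to the censoring rule, which stops such a subject being carried past the last visit or transmission.
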